1.1 Overview of disease pathogenesis, epidemiology and current treatment

Chronic iron overload represents a serious complication of potentially lifesaving blood transfusions which are the mainstay of therapy in transfusion-dependent anemias. Since humans have no mechanism for the active elimination of iron from the body, excess iron received via transfusions deposits in various tissues of the body, particularly the liver, heart and endocrine organs, leading to end-organ dysfunction and eventually organ failure. Indeed, organ failure due to chronic iron overload represents the major cause of death in patients with β -thalassemia major who receive blood transfusion regularly without appropriate chelation therapy (Cappellini et al, 2006).

Overview β -thalassemia

Beta-thalassemias are a group of hereditary blood disorders characterized by anomalies in the synthesis of the beta chains of hemoglobin resulting in variable phenotypes ranging from severe anemia to clinically asymptomatic individuals.

Beta-thalassemia is prevalent in the Mediterranean basin, the Middle East, Central Asia, India, Southern China, and the Far East, as well as countries along the north coast of Africa and in South America.

The total annual incidence of symptomatic individuals is estimated at 1 in 100,000 throughout the world and 1 in 10,000 people in the European Union. However accurate data on carrier rates in many populations are lacking.

Three main phenotypic forms have been described: thalassemia major, thalassemia intermedia and thalassemia minor with β -thalassemia major being the most severe form of the disease. Individuals with β -thalassemia major usually present within the first two years of life with severe anemia requiring regular red blood cell (RBC) transfusions. Findings in untreated or poorly transfused patients with thalassemia major are growth retardation, pallor, jaundice, poor musculature, hepatosplenomegaly, development of masses from extramedullary hematopoiesis, and skeletal changes that result from expansion of the bone marrow. If left untreated, 80% of β -thalassemia major patients die within the first 5 years of life due to anemia-related conditions. As such, transfusion therapy remains the mainstay of treatment in β -thalassemia major patients. Regular transfusion therapy leads to iron overload with iron-related complications including endocrine such as growth retardation, failure of sexual maturation, diabetes mellitus; cardiac such as dilated cardiomyopathy; and liver including fibrosis and cirrhosis.

The therapeutic concept of iron chelation has been established with more than 50 years of clinical experience with Desferal[®], deferoxamine mesylate, (DFO). However, poor oral bioavailability and short plasma half-life ($t_{1/2}$) has necessitated its application as slow subcutaneous (s.c.) or intravenous (i.v.) infusion. Iron-chelation therapy with DFO is extremely demanding however, and many patients experience considerable discomfort from administration of the drug, as well as a significant negative impact on their Quality of Life (QoL) (Arboretti et al, 2001) thus resulting in poor compliance. The lack of compliance with DFO

administration in patients who have serious blood disorders has necessitated recognition for the need of an effective iron chelator which can be given via the more convenient oral route.

Compliance with iron chelation therapy (ICT) mainly influences frequency and severity of iron overload-related complications (Galanello et al Origa 2010) with demonstrated improvement in organ dysfunction and survival in patients compliant with therapy (Gabutti et al 1996)

Transfusions and oral iron chelation therapy have dramatically improved the quality of life for patients with severe anemias. Previously a rapidly fatal disease in early childhood, β -thalassemia is now a chronic disease compatible with a prolonged life expectancy. Today, life expectancy varies between 25 and 55 years, depending on patient compliance with medical treatment, particularly iron chelation (Cappellini MD 2008)

1.2 Introduction to investigational treatment(s) and other study treatment(s)

1.2.1 Overview of deferasirox dispersible tablet:

The orally available tridentate iron chelator deferasirox (company research code ICL670) was first approved for the treatment of chronic iron overload due to blood transfusions in adults and pediatric patients aged 2 years and older in the United States in November 2005 and is currently approved for this indication in more than 100 countries. Deferasirox has also been approved in more than 60 countries for the treatment of chronic iron overload in patients with non-transfusion dependent thalassemia aged 10 years and older.

Deferasirox dispersible tablet (DT) is currently marketed as Exjade[®] in three dosing strengths (125, 250, and 500 mg) and is dosed based on body weight. The currently approved dose range is up to 40 mg/kg/day; the approved starting dose is 20 mg/kg/day. Initial daily doses of 10 or 30 mg/kg may be considered depending on treatment aim and transfusion intensity. Deferasirox DT is to be taken once daily on an empty stomach, at least 30 minutes before the next meal. Administration requires dispersion of the tablets in a glass of water, orange juice or apple juice, which takes approximately 3 minutes.

1.2.1.1 Non-clinical experience

Deferasirox is an N-substituted bis-hydroxyphenyl-triazole, a class of tridentate iron chelators. It is available as a dispersible tablet containing 125, 250, or 500 mg of drug substance. In certain countries, deferasirox is available as dispersible tablet containing 100 or 400 mg of drug substance. In addition, new formulations, such as swallowable film-coated tablets containing 90, 180 or 360 mg of drug substance and as oral granules corresponding to an amount equivalent to 90, 180 and 360 mg of drug substance, have also been produced.

The potent, specific ability of deferasirox to mobilize and promote the excretion of tissue iron has been demonstrated in animal models; it was twice as effective as parenteral deferoxamine (Desferal[®], DFO) and 5-fold more effective than deferiprone (Ferriprox[®]) in iron-loaded rats, and more than 10-fold as effective as deferiprone at equimolar doses in iron-loaded marmosets.

Deferasirox has been tested *in vitro* and *in vivo* in animal toxicology, carcinogenicity, and safety pharmacology studies. The compound was generally well tolerated and prohibitive toxicities

were not observed in rodent (rat) and non-rodent (marmoset) species. Many of the observed effects, particularly to the kidney, are considered to be a result of iron deprivation. No-adverse-effect-levels (NOAELs) in 4-week studies were 10mg/kg in rats (standard diet) and 65 and 130 mg/kg in male and female marmosets, respectively. The NOAELs in chronic studies were 30 mg/kg in rats (diet supplemented with iron) and 40 mg/kg in marmosets. Deferasirox had no effect on animal fertility and is not teratogenic. In rats and transgenic mice, no relevant carcinogenic potential has been observed.

1.2.1.2 Clinical experience

Orally administered deferasirox is rapidly and well absorbed in mice, rats, marmosets and dogs and metabolism is mainly by glucuronidation. Deferasirox and its iron complex are highly bound (>98%) to plasma proteins, and distribution is mainly intravascular. Key elimination processes are hepatic metabolism and hepato-biliary elimination ultimately into the feces. Mrp2-mediated active transport processes may be involved in the excretion of deferasirox and metabolites. No notable retention of ¹⁴C radioactivity was observed in the tissues of rats following [¹⁴C] deferasirox administration. The placental barrier was passed only to a low extent; however, because deferasirox and/or its metabolites can be transferred into milk, women are advised not to breast feed.

In β -thalassemia patients, peak plasma concentrations of deferasirox were achieved with a median T_{max} at between 1-4 hours at steady state and the mean terminal elimination half-life was in the range of 7-16 hours which support once daily administration. Following oral administration, the steady-state PK of deferasirox was dose-proportional over the dose range of 10-40 mg/kg (dispersible tablets). Clinical studies demonstrated a dose-dependent increase in iron excretion.

Metabolism is primarily by glucuronidation and elimination is mainly via the biliary/fecal route.

In clinical drug-drug interaction studies, deferasirox inhibited metabolism of the CYP2C8 substrate, repaglinide, and CYP1A2 substrate theophylline. No inhibitory effect on the CYP3A4 substrate midazolam was observed. The potent inducer of UGT and CYP isoenzymes, rifampicin led to a marked decrease of deferasirox exposure in humans. The absence of a drug interaction with digoxin was confirmed in humans.

Deferasirox dispersible tablet facilitates administration of the appropriate quantity of drug substance to pediatric and adult patients. Bioavailability studies with deferasirox dispersible tablets indicated that absorption is increased with food, and this is dependent on the fat content and the timing of food intake. Deferasirox dispersible tablet was taken on an empty stomach at least 30 minutes prior to food in clinical studies; this is also the recommendation in the label.

Deferasirox bioavailability was increased with the newly developed formulations (film-coated tablet and granule); therefore, equivalent deferasirox AUC was achieved at a lower dose with the new formulations (e.g., 1080 mg film-coated tablets vs. 1080 mg granules vs. 1500 mg dispersible tablets) although C_{max} was higher with the new formulations compared to the current formulation (dispersible tablets). The absence of a substantial food effect with the new formulations allowed patients to take the drug either on an empty stomach or with a light meal [ICL670F2101].

Results of a retrospective exposure-response analysis suggested that safety and efficacy of deferasirox are largely driven by overall exposure (AUC) and changes in C_{max} are unlikely to result in worsening renal laboratory values.

1.2.2 Overview of deferasirox film-coated tablet

Based on the chronic nature of chelation therapy and the importance of patient compliance, an improved deferasirox formulation for oral administration is being developed (company research code ICL670). The film-coated tablet (FCT) to be used in this study contains the same active substance but has been strength-adjusted to achieve comparable exposure to the currently approved dispersible tablet. The film-coated tablet (FCT) will be available in three dose strengths (90 mg, 180 mg and 360 mg) and is dosed based on body weight. The film-coated tablets can be taken with or without a light meal.

Deferasirox film-coated tablet (FCT) is already marketed in some countries like USA or Canada, as Jadenu[®].

Pharmacokinetics

Deferasirox film-coated tablets are a strength-adjusted formulation of deferasirox with higher bioavailability compared to the Exjade[®] dispersible tablet formulation. After strength-adjustment, the film-coated tablet formulation (360 mg strength) was equivalent to Exjade[®] dispersible tablets (500 mg strength) with respect to the mean area under the plasma concentration time curve (AUC) under fasting conditions [74]. The C_{max} was increased by 30% (90% CI: 20.3% - 40.0%); however a clinical exposure/response analysis has revealed no evidence of clinically relevant effects of such an increase.

Absorption

Deferasirox (dispersible tablet formulation) is absorbed following oral administration with a median time to maximum plasma concentration (t_{max}) of about 1.5 to 4 hours. The absolute bioavailability (AUC) of deferasirox (dispersible tablet formulation) was about 70% compared to an intravenous dose. The absolute bioavailability of the film-coated tablet formulation has not been determined. Bioavailability of deferasirox film-coated tablets was 36% greater than that with Exjade[®] dispersible tablets.

A food-effect study involving administration of the film-coated tablets to healthy volunteers under fasting conditions and with a low-fat (fat content <10% of calories) or high-fat (fat content >50% of calories) meal indicated that the AUC and C_{max} were slightly decreased after a low-fat meal (by 11% and 16%, respectively). After a high-fat meal, AUC and C_{max} were increased (by 18% and 29%, respectively). The increases in C_{max} due to the change in formulation and due to the effect of a high-fat meal may be additive and therefore, it is recommended that Deferasirox FCT should be taken either on an empty stomach or with a light meal

2 Rationale

2.1 Study rationale and purpose

The availability of deferasirox DT (Exjade[®]) as a once-daily oral chelation treatment provided patients with a treatment that was a significant improvement over parenteral deferoxamine therapy. This was confirmed in studies that measured satisfaction and quality of life of oral vs. parenteral chelation ([Cappellini et al 2007](#), [Osborne et al 2007](#))

Novartis has developed a film-coated tablet (FCT) with the same active substance as deferasirox DT but with modified excipients.

After strength-adjustment, the new formulation was shown to achieve the same overall exposure (AUC_{last} and AUC_{inf}) as the currently approved dispersible tablet formulation in a single-dose healthy volunteer study [ICL670F2102]; the peak serum concentrations (C_{max}) were approximately 30% higher. In addition, a food effect study [ICL670F2103] indicated that the FCT can be taken with a light meal (the current deferasirox DT has to be taken on an empty stomach, at least 30 mins before a meal).

The purpose of the present study is fully described on [Table 3-1](#).

2.2 Rationale for the study design

This is an open-label, multicenter, single arm, phase II study which will enroll patients with transfusion-dependent thalassemia and non-transfusion-dependent thalassemia.

Patient preference is the primary objective of this study and will be addressed by measuring the proportion of patient claimed preference of deferasirox FCT over deferasirox DT assessed by a preference questionnaire at Week 48

Patients previously treated with iron chelators for at least 6 months continuously (excluding deferasirox) or who are chelator naïve will be eligible to participate in this study.

The study consists of two phases. The treatment duration for the core phase of 48 weeks is considered sufficient to assess the patient preference, safety, compliance and PRO profiles of the two formulations. Previous studies of pediatric and adolescent patients have demonstrated differences in iron chelation medication compliance within this time period ([Jordan 2012](#), [Alvarez 2009](#)). The extension phase permits patients to continue receiving deferasirox FCT for a maximum of 12 months after completion of the core phase, or until one of the end of study criterion is met, whichever comes first.

Patient preference for different ICTs, satisfaction, palatability and GI symptoms will be assessed via validated questionnaires; overall safety, efficacy of deferasirox (both DT and FCT) and pill count will be assessed as secondary objectives. The subgroups of interest are the patients with transfusion-dependent or non-transfusion-dependent thalassemia, as well as ethnicity.

2.3 Rationale for dose and regimen selection

Deferasirox is available in three dosing strengths: 125, 250 and 500 mg for dispersible tablets and 90, 180 and 360 mg for film-coated tablets.

For each patient, the dose is calculated by the physician based on the patient's weight, and then rounded up or down to the nearest tablet configuration, which can result in a variance between the calculated and actual dose of up to 15%. This dosing paradigm is consistent with how deferasirox DT (Exjade[®]) has been developed with regard to safety and efficacy.

All Deferasirox naïve patient or chelation naïve patients or patients who have been treated by other chelators such as Deferiprone (DFP) / Deferoxamine (DFO) or Combination (DFO + DFP) for at least 6 months continuously, at the study entry will use a starting dose of:

- Deferasirox DT of 20 mg/kg/day in transfusion-dependent thalassemia (TDT)
- Deferasirox DT of 10 mg/kg/day in non-transfusion-dependent thalassemia (NTDT),

The equivalent FCT starting dose is:

- Deferasirox FCT of 14 mg/kg/day in transfusion-dependent thalassemia (TDT)
- Deferasirox FCT of 7 mg/kg/day in non-transfusion-dependent thalassemia (NTDT).

For patients with difficulties in swallowing Deferasirox FCT, it is allowed to crush the film-coated tablets. It should be administered by sprinkling the full dose on soft food like yogurt or apple sauce (apple puree). For further instructions, refer to the [Appendix 14](#).

Dose adjustments are permitted as follows:

- Patients receiving the DT formulation: \pm 5-10 mg/kg/day; maximum daily dose: 40 mg/kg/day for TDT patients; 20 mg/kg/day for NTDT patients
- Patients receiving the FCT formulation: \pm 3.5-7 mg/kg/day; maximum daily dose: 28 mg/kg/day for TDT patients; 14 mg/kg/day for NTDT patients.

For ICT naïve patients at study entry the dose can be adjusted after 4 weeks of study treatment and for ICT pre-treated patients, the dose should be adjusted if necessary every 3 months based on serum ferritin levels

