6.1.1 Dosing regimen

Having completed the screening period (including the 5-day wash-out period for patients previously treated with Deferiprone/DFP or Deferoxamine/DFO), eligible patients will start the core phase and be switched on the Day 1 visit to deferasirox DT for 24 weeks followed by deferasirox FCT for 24 weeks duration. Upon completion of Week 48 (Core Phase), the patient can still be treated with deferasirox FCT for a maximum of another 48 weeks or until one of the end of study criteria defined is met, whichever comes first.

The starting dose on Baseline Day 1 would be as following:

- Deferasirox DT of 20 mg/kg/day in transfusion-dependent thalassemia (TDT)
- Deferasirox DT of 10 mg/kg/day in non- transfusion-dependent thalassemia (NTDT),

Table 6-1 Equivalent FCT starting dose at Week 25

Equivalent dose to be used	
Deferasirox DT (mg/kg/day)	Deferasirox FCT (mg/kg/day)
5	3.5
10	7
15	10.5
20	14
25	17.5
30	21

Equivalent dose to be used	
Deferasirox DT (mg/kg/day)	Deferasirox FCT (mg/kg/day)
35	24.5
40	28

All iron chelation pre-treated patients who had received treatment with deferoxamine (DFO) and deferiprone (DFP) will be initiated on deferasirox DT. The dose of deferiprone will be determined by their serum ferritin and the dose of deferoxamine by using the equivalent deferasirox DT dose (see [Appendix 14.2](#)).

Dose adjustment for better treatment effects, based on serum ferritin levels and investigator's judgment, will be allowed for ICT naïve patients after 4 weeks of study treatment and for ICT pre-treated patients every 3 months. The dose adjustments will be performed in steps of 5-10 mg/kg/day for deferasirox DT or in steps of 3.5-7 mg/kg/day for deferasirox FCT.

For each patient the daily dose is calculated by the physician based on the patient's actual body weight, and then rounded up or down to the nearest whole tablet according to the available strengths of deferasirox tablets (125 mg, 250 mg and 500 mg for the DT and 90 mg, 180 mg and 360 mg for the FCT, see [Appendix 14.1](#)).

The investigator should instruct the patient (or legal patient's representative in the case of pediatric patients) to take the study drug as prescribed. All doses planned and prescribed to the patient and all dose changes including reasons for change during the study must be recorded in the eCRF.

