Dose adjustments based on safety are allowed at any time point in the study and will be in increments of 5-10 mg/kg/day for deferasirox DT or 3.5-7 mg/kg/day for deferasirox FCT. Dose adjustments based on efficacy are permitted. For ICT naïve patients at study entry dose adjustments are allowed after 4 weeks of study treatment based on serum ferritin levels and investigator's judgement. For ICT pre-treated patients, the dose of deferasirox should be adjusted if necessary every 3 months based on the trends in serum ferritin and investigator's judgement. For more details please refer to [Table 6.2](#) – Dose of study drug based on serum ferritin level.

Table 6-2 Dose and treatment schedule

Study treatments	Pharmaceutical form and route of administration	Starting Dose* (weeks 1-4)	Dose adjustment (after week 4)	Max dose	Frequency and/or Regimen
Deferasirox DT – TDT patients	Dispersible tablets, p.o.	20 mg/kg/day	+ 5 - 10 mg/kg/day	40 mg/kg/day	Once daily
Deferasirox DT – NTD patients	Dispersible tablets, p.o.	10 mg/kg/day	+ 5 - 10 mg/kg/day	20 mg/kg/day	Once daily
Deferasirox FCT – TDT patients	Film-coated tablets, p.o.	14mg/kg/day	+ 3.5 - 7 mg/kg/day	28 mg/kg/day	Once daily
Deferasirox FCT – NTD patients	Film-coated tablets, p.o.	7 mg/kg/day	+ 3.5 - 7 mg/kg/day	14 mg/kg/day	Once daily

*Iron chelation naïve patients. All iron chelation pre-treated patients see [Section 6.1.1](#) and [Appendix 14.2](#) for guidance.

Table 6-3 Daily dose of study drug based on serum ferritin level

Dose Regimen of Drug for TDT patients	Serum ferritin level
20 mg/Kg Deferasirox DT 14 mg/Kg Deferasirox FCT	1000-1500 ng/ml
30 mg/Kg Deferasirox DT 21 mg/Kg Deferasirox FCT	>1500-2000 ng/ml
40 mg/Kg Deferasirox DT 28 mg/Kg Deferasirox FCT	>2000 ng/ml
Dose Regimen of Drug for NTD patients	Serum ferritin level
5 mg/Kg Deferasirox DT 3.5 mg/Kg Deferasirox FCT	300-799 ng/ml
10 mg/Kg Deferasirox DT	800-2000 ng/ml

Dose Regimen of Drug for TDT patients	Serum ferritin level
7 mg/Kg Deferasirox FCT	
20 mg/Kg Deferasirox DT 14 mg/Kg Deferasirox FCT	>2000 – 4000 ng/ml
30mg/Kg Deferasirox DT 21mg/Kg Deferasirox FCT	>4000ng/mL

Serum ferritin level will be measured monthly to evaluate the study drug response

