7.1.2 Treatment period

The duration of core phase treatment is 48 weeks. Patient visits will occur every 2 weeks during the first month of treatment and then every 4 weeks thereafter until Visit 777 (SEC).

Having completed the screening period (including the 5-day wash out period for patients previously treated with deferiprone (DFO) or deferoxamine (DFP)), patients who are eligible will be enrolled to receive deferasirox DT during 24 weeks then switch to deferasirox FCT for 24 weeks. Daily dose is calculated by the physician based on the patient's actual body weight.

At the start of treatment, iron chelation naïve patients will receive deferasirox DT 10 mg/kg (NTDT patients) or 20 mg/kg (TDT patients) once daily then will transition to the equivalent FCT dose as outlined in the following table.

Table 7-3 Equivalent dose to be used: Deferasirox DT vs Deferasirox FCT

Equivalent dose to be used	
Deferasirox DT (mg/kg/day)	Deferasirox FCT (mg/kg/day)
5	3.5
10	7
15	10.5
20	14
25	17.5
30	21
35	24.5
40	28

All iron chelation pre-treated patients will follow the below guidance:

Patients who were taking deferoxamine (DFO), will need to take the deferasirox DT equivalent deferasirox. For deferiprone (DFP) the dose of deferasirox DT will be based on their serum ferritin. Please refer to [Table 6-2](#).

At the Week 48 visit, patients will roll over to the extension phase in the case that none of the End of Study criteria is met at that time. The patient will receive deferasirox FCT following the same dose regulations and adjustments as per the core phase.

The treatment period of the extension study is approximately 52 weeks (including treatment period (48 weeks), Study Evaluation Completion and 4 weeks Safety Follow-up visits)

For details on study design and dose adjustments, see [Section 4](#) and [Section 6.3](#).

For details of assessments, see [Table 7-1](#) and [Table 7-2](#).

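### The protocol gives two different starting doses to patients previously treated with another chelator and two different maximum doses to NTDT patients, and the SAP's per-protocol rules inherit both conflicts

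*Protocol*

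**What the plan says.** **Fixed start.** Protocol Section 2.3 groups naïve patients with "patients who have been treated by other chelators such as Deferiprone (DFP) / Deferoxamine (DFO") or the two combined, and says those treated "for at least 6 months continuously, at the study entry will use a starting dose of" DT 20 (TDT) or 10 (NTDT) mg/kg/day. Section 6.1.1 lists the same Day 1 doses without limiting them to any group.

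**Naïve-only start.** Section 7.1.2 says "iron chelation naïve patients will receive deferasirox DT 10 mg/kg (NTDT patients) or 20 mg/kg (TDT patients"). The asterisk on the starting-dose column of Table 6-2 reads "Iron chelation naïve patients. All iron chelation pre-treated patients see" Section 6.1.1 and Appendix 14.2.

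**Pre-treated rule.** Section 6.1.1: "The dose of deferiprone will be determined by their serum ferritin and the dose of deferoxamine by using the equivalent deferasirox DT dose". Section 7.1.2: "For deferiprone (DFP) the dose of deferasirox DT will be based on their serum ferritin". Appendix 14.1 sets the DT start at half the DFO dose (Table 14-18) and bases the dose after DFP on ferritin (Table 14-17).

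**NTDT maximum.** The protocol summary, Section 2.3, Table 6-2 and Section 6.2.1.3 give DT 20 / FCT 14, and 6.2.1.3 does not permit more. The NTDT row above 4000 ng/ml in Tables 6-3 and 14-17 is DT 30 / FCT 21.

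**Design outline.** Protocol Section 4.1 gives DT 20-40 and FCT 14-28 for everyone. SAP Section 1.1 gives 10-40 and 7-28.

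**Per-protocol rules (SAP 5.5, Table 1).** S01, S03, S08, S09, S10, S15 and S16 each exclude from the per-protocol set (PPS).

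**The concern.** Followed literally, the protocol gives one pre-treated patient two starting doses, and gives an NTDT patient above 4000 ng/ml a table dose that another section forbids. Section 1.2.1.2 describes safety and efficacy as driven largely by exposure, and the trial enrols from age 2, so a dosing ambiguity matters even in a preference study. The outline in Section 4.1 does not help: its lower bounds (20/14) are the NTDT maximum.

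The statistical consequence is narrower. The PPS rules test dose against several of these tables at once. Where the tables disagree, a patient treated exactly as one rule requires is a major deviator under another.

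**Working it through.** **1. Starting-dose rules side by side**

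| Place | Who gets 20/10 | Prior DFO | Prior DFP | DFO+DFP |
|---|---|---|---|---|
| 2.3 | everyone | 20/10 | 20/10 | 20/10 |
| 6.1.1 | Day 1 list, unrestricted | DFO-equivalent | by ferritin | no rule |
| Table 6-2 footnote | naïve only | refers elsewhere | refers elsewhere | no rule |
| 7.1.2 | naïve only | DFO-equivalent | by ferritin | no rule |
| Appendix 14.1 | not stated | half the DFO dose | by ferritin | no rule |

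Inclusion criterion 3c admits DFO+DFP, but only Section 2.3 gives those patients a start.

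**2. Size of the starting-dose conflict.** Ratio = Section 2.3 dose / dose by the pre-treated rule, in DT mg/kg/day.

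- TDT, prior DFO 10, 20, 30, 40, 50, 60, 70, 80 (DT = DFO/2 = 5, 10, 15, 20, 25, 30, 35, 40): 20/5 = 4; 2; 1.33; 1; 0.8; 0.67; 0.57; 20/40 = 0.5.
- NTDT, prior DFO 10, 20, 30, 40 (DT 5, 10, 15, 20): 10/5 = 2; 1; 0.67; 10/20 = 0.5. DFO 50 to 80 converts to DT 25 to 40, above the stated maximum of 20.
- TDT, prior DFP, ferritin 1000-1500, >1500-2000, >2000 (DT 20, 30, 40): 1; 0.67; 0.5.
- NTDT, prior DFP, ferritin 800-2000, >2000-4000 (DT 10, 20): 1; 0.5. Above 4000: 10/30 = 0.33 by the table, or 10/20 = 0.5 at the maximum.

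In tablets, a 20 kg TDT child after DFP with ferritin above 2000 gets 375 mg at 20 mg/kg (Table 14-4) against 750 mg at 40 mg/kg (Table 14-8): 750/375 = 2.

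**3. NTDT maximum.** Row above 4000 ng/ml against the stated maximum: 30/20 = 1.5 for DT and 21/14 = 1.5 for FCT.

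**4. Cross-references**

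- 6.1.1 and the Table 6-2 footnote cite Appendix 14.2, which is light-meal examples. The DFO table is in Appendix 14.1.
- 6.1.1 cites Table 6.2 under the description "Dose of study drug based on serum ferritin level", which is Table 6-3. Section 7.1.2 cites Table 6-2 for the ferritin-based DFP dose.
- Appendix 14.1 cites Table 14-17 (ferritin) for DFO conversion, which is Table 14-18.

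Those five are plainly wrong. A sixth, Table 6.2 in Section 6.2.1.3, is probably wrong: the sentence before it concerns ferritin trends, but Table 6-2 does hold adjustment steps and maxima.

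**5. What the SAP rules do with this**

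- NTDT, ferritin above 4000: S03 (Table 6-3) requires DT 30, while S15 (Table 6-2 maximum) allows at most 20. No DT dose meets both. For FCT, S03 requires 21 and S16 allows 14.
- Naïve TDT, ferritin >1500-2000: S01 requires 20, S03 requires 30, and S09 flags a non-safety change before 4 weeks.
- TDT, prior DFO 40, ferritin above 2000: S08 requires 40/2 = 20, S03 requires 40, and S10 flags a non-safety change before 3 months.

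S03 has no exemption for starting doses. All these rules carry code 4 (PPS only). The full analysis set (FAS) is removed by codes 1 and 3, so FAS membership does not change.

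**The case against.** Section 2.3 is a rationale section, the pre-treated rule is repeated in three other places, and a careful investigator would follow those. The dose tables are framed as guidance subject to the investigator's judgement. The appendix's own example, DFO 40, converts to DT 20, exactly the Section 2.3 TDT start. Several wrong references do little harm: one describes the right table, and Table 14-18 sits directly beneath a line pointing to it.

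Much of this stands, and it limits the clinical risk. It does not dispose of the point. Section 6.1.1, which is treatment text, also lists the fixed start unrestricted, and Section 6.2.1.3 is a prohibition that Table 6-3 contradicts. The SAP also turns the guidance into grounds for exclusion.

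Some stronger readings are tempting, but the documents do not support them:

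- *Section 2.3 is the lone outlier.* Section 6.1.1 shares the fault, and the treatment sections disagree on the NTDT maximum.
- *DFO+DFP has no start anywhere.* Section 2.3 gives one; the other sections do not.
- *S08 misapplies equivalence to DFP.* It points to Appendix 14.1, whose equivalent-dose guidance covers both the DFO and the DFP rule.
- *20/14 is certainly the intended NTDT maximum.* The Amendment 1 rationale cites NTDT data at up to 30 mg/kg/day, so the 30/21 row may be deliberate.
- *Only about 13 starts remained (145 - 132).* The glossary defines enrolment at consent, so 132 need not be patients started, and Table 6-3 also guides adjustment after the start.

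**Conclusion.** The conflict is real on the current text and should be fixed. With the stated NTDT maximum applied, the starting-dose discrepancy is 2-fold or less in every row except TDT after DFO 10, the lowest conversion row, where it is 4-fold. If the 30/21 row stands, NTDT patients after DFP above 4000 ng/ml face a 3-fold gap (30/10). The NTDT maximum itself differs by a factor of 1.5. The documents give no distribution of prior DFO dose, prior DFP use or ferritin, so the number affected is unknown and 4-fold should not be read as typical.

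The PPS effect assumes that S03 is applied as written, from the first dose. On that reading, correctly started naïve patients and correct DFO conversions are excluded whenever ferritin calls for a higher dose, and NTDT patients above 4000 ng/ml cannot comply at all. A reader might infer that the primary result is at risk. It is not: McNemar's test runs on the FAS, SAP 2.5.4 makes the PPS analysis supportive, and the sample size does not use dose.

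**What to change.** **Protocol**

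- In 2.3 and the Day 1 list in 6.1.1, limit the fixed start to chelation-naïve patients. Send prior DFO to Table 14-18 and prior DFP to Table 6-3/14-17.
- Have the sponsor state the start for DFO+DFP; the documents do not settle it.
- State one NTDT maximum everywhere. Either cap the rows above 4000 ng/ml at 20/14, or raise the maximum to 30/21 in the summary, 2.3, Table 6-2 and 6.2.1.3. Either way, say that it also bounds Table 14-18 for NTDT patients.
- Correct the five references, and the sixth if Table 6-3 is meant.
- In 4.1, give starting and maximum doses by TDT and NTDT as in the summary, with the start marked as the naïve start in both places. Ranges with a lower bound would exclude permitted doses, such as DT 5 after DFO 10 in TDT or DT 5 for NTDT at 300-799 ng/ml.

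**SAP**

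- State that S03 does not apply to a correct naïve start or DFO conversion before the first permitted adjustment, and that it uses the reconciled NTDT maximum. S08 needs no change.

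**Cost.** Protocol wording, one SAP rule and two sponsor decisions (NTDT maximum and DFO+DFP start). There is no change to data collection, the primary analysis or the sample size. The SAP's history shows entries after the interim database lock, the point at which the primary analysis is done. A change to S03 now would therefore alter PPS membership after that lock, and should be dated and reported with the PPS result under both versions.
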